6.1.2 STUDY EVALUATIONS AND PROCEDURES

Once eligibility has been confirmed, the subject will be randomized to receive study treatment. Visit dates and windows must be calculated from Day 0.

DAY 0

The following evaluations will be performed at Day 0 prior to study treatment:

- Determination of eligibility per inclusion/exclusion criteria
- Randomization .
- Targeted physical assessment •
- Vital signs including weight

Version Date: 01Jun2022

CONFIDENTIAL

Version 4.1

Page 52 of 87

Urine pregnancy test

- 2 digene[™] cervical brush samples •
- ThinPrepTM sample for HPV typing and pap smear (subject should be requested to abstain from any sexual activity and refrain from use of douching or vaginal lubricants/medication for a period of 24 hours prior to sample collection)
- Oropharynx (OP) sample by oral rinse and vaginal swabs for HPV testing
- Intra-anal swab (if subject has consented to intra-anal sampling) for HPV testing
- Colposcopy
- Study treatment administration

The following evaluations will be performed on Day 0 post-t eatment:

- Post treatment adverse event and injection site reactio asses ment at least 30 minutes after study treatment
- Distribute Participant Diary Card (PDC)

**Please remember to download EP data from de ace within 24-48 hours of study treatment. **

8-14 DAYS POST DOSE 1 PHONE CALL

The following information will be evaluated during phone call:

- Post treatment adverse event and injection site reaction evaluation
- Review Day 0 PDC (after reviewing the PDC and post reatment injection assessment with the subject on the phone, the investigator or study personnel will determine whether an office visit is needed for further evaluation)

WEEK 4 (±4 DAYS)

The following study evaluation will be perfor med at Week 4 prior to study treatment:

- Targeted physical assessment •
- Vital signs including weight .
- Urine pregnancy test
- Collect PDC for dose 1
- Study treatment will be administered •

The following study evaluations will be performed at Week 4 post treatment:

- Post treatment adverse event and injection site reaction assessment at least 30 minutes after study . treatment:
- Distribute PDC

**Please remember to download EP data from device within 24-48 hours of study treatment. **

8-14 DAYS POST DOSE 2 PHONE CALL

The following information will be evaluated during phone call:

Version Date: 01Jun2022

CONFIDENTIAL

Version 4.1

Page 53 of 87

- Post treatment adverse event and injection site reaction evaluation
- Review Week 4 PDC (after reviewing the PDC and post treatment injection assessment with the subject on the phone, the investigator or study personnel will determine whether an office visit is needed for further evaluation)

WEEK 8 (±4 DAYS)

The following study evaluation will be performed during the visit:

- Targeted physical assessment
- Vital signs
- Collect and review PDC for dose 2
- Post treatment adverse event and injection site reaction evaluation
- ThinPrep[™] sample for HPV typing and pap smear (subject should be requested to abstain from any sexual activity and refrain from use of douching or vaginal lubricants/medication for a period of 24 hours prior to sample collection)

WEEK 12 (±4 DAYS)

The following study evaluation will be performed on Week 12 prior to study treatment:

- Targeted physical assessment
- Vital signs including weight
- Urine pregnancy test
- Study treatment will be administered

The following study evaluations will be performed at Week 12 post treatment:

- Post treatment adverse event and njec ion site rection assessment within a minimal of 30 minutes after study treatment
- Distribute PDC

**Please remember to download EP data from device within 24-48 hours of study treatment. **

8-14 DAYS POST DOSE 3 PHONE CALL

The following informatio will be evaluated during phone call:

- Post treatment adverse event and injection site reaction evaluation
- Review Week 12 PDC (after reviewing the PDC and post treatment injection assessment with the subject on the phone, the investigator or study personnel will determine whether an office visit is needed for further evaluation.)

WEEK 15 (± 1 WEEK)

The following study evaluations will be performed at Week 15:

- Targeted physical assessment
- Vital signs
- Post-treatment injection site reaction assessment
- Urine pregnancy test

Version Date: 01Jun2022

CONFIDENTIAL

Version 4.1

Page 54 of 87

- 2 digene[™] cervical brush samples
- ThinPrep[™] sample for HPV typing and pap smear (subject should be requested to abstain from any sexual activity and refrain from use of douching or vaginal lubricants/medication for a period of 24 hours prior to sample collection)
- Colposcopy
- Collect PDC

WEEK 28

The following study evaluations/actions will be performed on Week 28 ± 1 week:

- Targeted physical assessment •
- Vital signs .
- Urine pregnancy test •
- 2 digene[™] cervical brush samples
- ThinPrep[™] sample for HPV typing and pap smear (sub ect should be requested to abstain from any sexual activity and refrain from use of douching or vagin Autor ants/medication for a period of 24 hours prior to sample collection)
- Colposcopy to assess for possible disease progression

WEEK 36

The following study evaluations will be performed on Week 36 ± 1 week:

- Targeted physical assessment
- . Vital signs
- Socio-behavioral assessment (change in smoking, alcohol intake or recreational drug use from baseline) •
- Urine pregnancy test
- 2 digene[™] cervical brush samples
- ThinPrep[™] sample for HPV typing and pap smear (subject should be requested to abstain from any sexual activity and refr in from use of douching or vaginal lubricants/medication for a period of 24 hours prior to sample collection)
- Oropharynx (OP) sample by oral rinse and vaginal swabs for HPV testing •
- Intra-anal swab (if subject has consented to intra-anal sampling) for HPV testing .
- Colposcopy
- Surgical excision to be used for histopathologic assessment .

WEEK 40 (STUDY CONCLUSION)

The following study evaluations will be performed on Week 40 ± 2 weeks:

- **Complete Physical Examination**
- Vital signs .
- Socio-behavioral assessment (change in smoking alcohol intake or recreational drug use from baseline) .
- Urine pregnancy test
- Colposcopy .

Study Conclusion

Version Date: 01Jun2022

CONFIDENTIAL

Version 4.1

Page 55 of 87

6.2 INFORMED CONSENT

All subjects must sign the informed consent prior to any study related procedures being performed. The informed consent documentation must be in accordance with applicable regulations and Good Clinical Practice (GCP). Qualified study personnel will meet with prospective study participants, explain the study, and provide them with an informed consent form (ICF) that describes the screening tests, eligibility criteria for entering the study, study treatments and follow-up procedures, in a language understandable to the subject. Explanation of the study includes, but is not limited to, study objectives, potential benefits and risks, discomforts/inconveniences, and the subject's rights and responsibilities. The subject or subject's legally acceptable representative is then requested to sign and date the ICF. A copy of the signed informed consent documentation must be provided to the subject or subject's legally acceptable representative. The qualified study personnel will document the process of obtaining informed consent within the source record. Signed ICFs are maintained in the subject's source records and must be accessible for verification at any time.

6.3 ASSIGNMENT OF SUBJECT IDENTIFICATION NUMBERS

Each subject who consents will be assigned a unique subject identification number (SID), which identifies the subject for all study-related procedures. Once assigned, SIDs car ot be reused for any reason. Information regarding the SID and screen date ill be documented on a screening and enrollment log/system and in the eCRF.

Subjects meeting eligibility criteria listed in the protocol will be randomized by a computer-generated allocation schedule.

6.4 SAFETY EVALUATIONS

6.4.1 PHYSICAL EXAMINATION

A complete physical examination (Pc) will be inducted during screening and study discharge. It will include an assessment of the following: general appearance, skin, head, eyes, ears, nose, and throat, lymph nodes, respiratory, cardiovascular, gastrointestinal, genitourinary, musculoskeletal, and neurological systems.

A targeted physical assessment will be performed at other visits as determined by the investigator or directed per subject complaints.

6.4.2 VITAL SIGNS

Vital signs will be measured at specified visits and will include:

- Sitting systolic and diastolic blood pressures with subject sitting at rest for at least 5 minutes before measurement
- Respiration rate
- Heart rate
- Oral temperature measured with an automated thermometer

6.4.3 HEIGHT AND WEIGHT

Height and weight will be collected at Screening and on Day 0, Weeks 4 and 12.

Version Date: 01Jun2022

CONFIDENTIAL

Version 4.1

Page 56 of 87

The BMI at the Day 0 visit will be used to determine the BMI stratum for randomization.

6.4.4 MEDICAL HISTORY

All relevant past and present conditions at screening, as well as prior surgical procedures will be recorded for the main body systems (as judged by the investigator). The medical history will include

a) Any prior history of CIN diagnosed – with diagnosis date(s) and respective CIN level(s),

b) If treated previously for CIN, the respective treatment type(s) and date(s).

6.4.5 SOCIO-BEHAVIORAL ASSESSMENT

Socio-behavioral assessment, including self-reported smoking history, history of exposure to second-hand smoke, alcohol intake history, recreational drug use, contraceptive use and type of contraceptive if known, reproductive history, history of prior cervical dysplasia, and pregnancy history will be obtained at Screening, Weeks 36 and 40. Socio-behavioral assessmen , erformed to document any change from Screening.

6.4.6 LABORATORY EVALUATIONS

At Screening, blood samples will be taken to be te red for serum chemistry and hematology:

Complete blood count (CBC):

- White blood cell (WBC) count with differential
- Red blood cell (RBC) count
- Hemoglobin, Hematocrit
- Platelet count

Serum Chemistry:

- Albumin
- Glucose
- Serum glut nic-pyruvic transaminase (SGPT)/Alanine aminotransferase (ALT)
- Blood urea nitro EA B N)
- Creatinine
- Electrolytes (Sodium, Potassium, Chloride, Carbon Dioxide or Bicarbonate)
- Creatine Phosphokinase (CPK)

6.4.7 URINALYSIS (UA)

Urine samples will be tested at screening by dipstick for glucose, protein, and hematuria. If abnormal (presence of protein, hematuria, or glucose $\geq 1+$) a microscopic examination should be performed.

6.4.8 DEMOGRAPHICS

Demographic information will be collected via self-report (unless noted otherwise), including the following:

- Age
- Race/ethnicity

Version Date: 01Jun2022

CONFIDENTIAL

Version 4.1

Page 57 of 87

• Dominant hand

6.4.9 URINE PREGNANCY TESTING

For subjects of reproductive potential, a negative spot urine pregnancy test is required prior to each study treatment, colposcopy and surgical excision. A final pregnancy test will also be done at Week 40 to capture pregnancy status at study completion.

6.4.10 ECG

A single 12-lead ECG will be obtained during Screening after the subject has been in a supine position for at least 10 minutes. The ECG should include measurements of ventricular rate, PR, QRS, QRS axis, QT, QTcb or QTcf, ST segment, T wave as well as an investigator assessment of whether the ECG is normal or abnormal (automated interpretations of ECG should not be used). Abnormal ECGs should be interpreted as "clinically significant (CS)" or "not clinically significant (NCS)" by the investigator.

6.4.11 PARTICIPANT DIARY CARD (PDC) SUBJECT SELF EVALUATION

Subjects will be provided and trained on a PDC and w 1 be asked to record the following the evening of study treatment through Day 6:

- Oral temperature and time taken (before 11:59 pm)
- General symptoms of feeling unwell
- Pain and itching at injection site
- Measure redness, swelling, bruising at injection site
- Medications taken

The completed PDC will be reviewed with the subject by the study staff at the 8 -14 day post-dose phone call and at the next in-person visit.

The study staff will review the PDC for general r mptoms (e.g. malaise, fatigue, headache, nausea, and myalgia/arthralgia), injection site reaction symptoms (e.g. pain, erythema and edema), medical events and medications.

Any PDC entry determined to meet the CTCAE criteria for a Grade 1 or higher adverse event should be documented as an adverse ev nt wless deemed part of the subject's ongoing medical history. If the PDC entry does not meet the criteria o `a Grade 1 or higher AE as per the CTCAE guidelines, clinical judgment can be used to determine whether the entry should be recorded as an AE and documented accordingly in the site's source. For cases where the PDC entry and final AE reporting (i.e. grading) do not agree, the reasoning should be recorded in the source documents.

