3.5 SAFETY ASSESSMENT

The safety monitoring plan is based upo 1 t e Phase 2b HPV-003 study results and the design of the Phase 3 HPV-301 study. Longer term ollow-up data of approximately 1.5 years after the last dose has been collected and reported in the HPV-003 Clinical Study Report. Longer term safety data will also be collected through approximately 1.5 years after the last do e in the HPV-301 Phase 3 study. The HPV-303 study has been designed to follow participants for approximately 7 months following their last dose of study treatment to serve as an independent second pivotal demonstration of the efficacy of VGX-3100.

Safety monitoring will include:

- Local and systemic events for 7 days following each treatment as noted on a Participant Diary Card (PDC).
- All adverse events including SAEs, UADEs, and other unexpected AEs for the duration of the study;

In HPV-003, the safety profile was carefully evaluated and treatment with VGX-3100 was well-tolerated based on observations through Week 88 in all subjects. The most common adverse events were administration-site reactions, which included pain, tenderness, erythema and swelling, and were generally mild and limited to a few days in duration. Only erythema showed a statistically higher incidence in VGX-3100 (78%) vs. placebo (57%) in the 7- and 28-day periods after a dose. Over the course of the entire 88 week study, sinusitis was statistically more commonly observed in the VGX-3100 group (10%) than in the placebo group (0%), but resolved without sequelae.

Version Date: 01Jun2022

CONFIDENTIAL

Version 4.1

Page 34 of 87

Downloaded by
Histology is the gold standard for the diagnosis of cervical HSIL. Therefore, the definitive histopathologic assessment in the Phase 2b study was determined by an independent blinded Pathology Adjudication Panel, comprised of experienced cytopathologists from independent medical centers in the US, who are also adjudicating the HPV-301 study. This will enable the highest certainty of the diagnosis for study entry with the exclusion of individuals with carcinoma and also enable a consistent and accurate histologic endpoint evaluation.

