4.3 DISCONTINUATION/WITHDRAWAL OF STUDY SUBJECTS

Subjects who manifest Grade 4 toxicity attributable to the study treatment will be discontinued from the study treatment. Subjects will not receive further study treatment but will be encouraged to continue safety follow-up assessments through study disc arge and not discontinue from the study.

If a subject manifests Grade 3 toxicity attributable to the study treatment, the Medical Monitor and investigator will discuss whether further treatment should be continued for that subject.

All randomized subjects should be encouraged to complete all study treatments and follow-up visits. A subject will be considered to have completed the study when she completes all scheduled study treatments and follow-up visits. However, a subject may voluntarily withdraw from study participation at any time or be withdrawn at any time at the discretion of the investigator for any maternal obstetrical or medical complications after consultation with the Medical Monitor.

Should a subject fail to attend the clinic for a required study visit, the site should attempt to contact the subject and reschedule the missed visit as soon as possible. The site should also counsel the subject on the importance of maintaining the assigned visit schedule for follow-up and treatment of HSIL (CIN2, CIN3), to ascertain whether or not the subject wishes to and/or should continue in the study based on previous noncompliance. In cases where the subject does not return for the rescheduled visit or cannot be reached to

Version Date: 01Jun2022

CONFIDENTIAL

Version 4.1

Page 41 of 87

reschedule the missed visit, the site should make every effort to regain contact with the subject (3 telephone calls and if that fails, then a certified letter to the subject's last known mailing address). If these attempts to contact the subject are unsuccessful the subject can be considered as withdrawn from the study (i.e. lost to follow-up). If contact with the subject is re-established, the site should contact the Medical Monitor to discuss whether the subject can continue study treatment or follow-up visits for the study. For all other subjects withdrawing from the study, an alternative reason for discontinuation should be recorded in the eCRF.

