6.9 ASSESSMENT OF INJECTION SITE REACTIONS

When evaluating injection site reactions throughout the study, the investigator will be instructed to use the following grading scale in Table 13.

Version Date: 01Jun2022

CONFIDENTIAL

Version 4.1

Page 60 of 87

Table 13: Grading Scale for Injection Site	Reactions
---	-----------

Local Reaction to Injectable Product (Grade)	Mild (1)	Moderate (2)	Severe (3)	Potentially Life Threatening (4)
Pain Does not interfere with activity		Repeated use of non- narcotic pain reliever >24 hours or interferes with activity Any use of narcotic pain reliever or prevents daily activity***		Emergency room (ER) visit or hospitalization
Tenderness Mild discomfort to touch		Discomfort with movement	Significant discomfort at rest	ER visit or hospitalization
Erythema/Redness*	2.5-5 cm	5.1-10 cm	>10 cm	Necrosis or exfoliative dermatitis
Induration/Swelling** 2.5-5 cm ar does not inter with activit		5.1-10 cm or interferes with activity	>10 cm or prevents daily activity	Necrosis

September 2007 "FDA Guidance for Industry—Toxicity Grading Scale for Healthy Adult and Adolescent Volunteers Enrolled in Preventive Vaccine Clinical Trials".

*In addition to grading the measured local reaction at the greatest single diameter, the measurement should be recorded as a continuous variable.

Inducation/Swelling should be evaluated and graded using the functional scale as well as the actual measurement $*Daily activity = Impact lasting \ge 24 hours$

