7.6 ASSESSING SEVERITY (INTENSITY)

Adverse events should be captured once on the CRF at ta massion m severity reported.

The investigator will grade laboratory AEs wit respect to the follo ing levels of severity as defined in the document "Toxicity Grading Scale" for appli_able patient populations:

- Mild (Grade 1)
- Moderate (Grade 2)
- Severe (Grade 3)
- Potentially Life Threatening (Grade 4)
- Death (Grade 5)

The investigator will grade clinical AEs or SAEs (based on discussions with study participants) in accordance with the Com for Terminology Criteria for Adverse Events (CTCAE) v 4.03.

The investigator will grade injection site reactions in accordance with September 2007 FDA Guidance for Industry – Toxicity Grading Scale for Healthy Adult and Adolescent Volunteers Enrolled in Preventive Vaccine Clinical Trials.

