- DD-UNK-YYYY; if DD and YYYY are the same as that of 1st dose, then impute to same date as 1st dose; otherwise impute to DD-JAN-YYYY;
- DD-MMM-UNKN; if DD and MMM are the same as that of 1st dose, then impute to same date as 1st dose; otherwise impute to DD-MMM-YOSCR, where YOSCR is year subject was initially screened;
- UK-UKN-YYYY: if YYYY is the same as that of 1st dose, then impute to same date as 1st dose; otherwise impute to impute to 01-JAN-YYYY;
- UK-MMM-UNKN: if MMM is the same as that of 1st dose, then impute to same date as 1st dose; otherwise impute to 01-MMM-YOSCR, where YOSCR is year subject was initially screened;
- DD-UNK-UNKN: if DD is the same as that of 1st dose, then impute to same date as 1st dose; otherwise impute to impute to DD-JAN-YOSCR, where YOSCR is year subject was initially screened;
- UK-UKN- UNKN: impute to date of subject's 1st dose.

If the imputed start date is after the raw stop date, then the imputed start date will be set as the same as the stop date.

Missing stop dates will be handled as follows (where UK, UKN and UNKN indicate unknown or missing day, month and year respectively):

- UK-MMM-YYYY: impute to the last day of the month;
- DD-UNK-YYYY: impute to DD-DEC-YYYY;
- DD-MMM-UNKN: impute to DD-MMM-YOLV, where YOLV is year of subject's last study visit;
- UK-UKN-YYYY: impute to 31-DEC-YYYY;
- UK-MMM-UNKN: impute to LD-MMM-YOLV, where LD is the last day of MMM and YOLV is year of subject's last study visit;

- DD-UNK-UNKN: impute to DD-DEC-YOLV, where YOLV is year of subject's last study visit;
- UK-UKN- UNKN: impute to day of subject's last study visit.

If the imputed stop date is before the raw or imputed start date, then the imputed stop date will be set as the same as the start date.

AE duration will be calculated as (Stop Date – Start Date) + 1.

AE summary tables will include numbers and percentages of subjects experiencing at least one event by treatment arm. The following is a list of AE summary tables to be generated:

- Overview of AE, AE with onset within 28 days/7 days after study treatment
- TEAEs, TEAEs with onset within 28 days/7 days after study treatment by SOC and PT
- TEAEs, TEAEs with onset within 28 days/7 days after study treatment by Dose Number, SOC and PT
- TEAEs, TEAEs with onset within 28 days/7 days after study treatment by Dose Number, CTCAE Grade, SOC and PT
- Serious TEAEs by Dose Number, SOC and PT

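### Injection-site reactions are graded on the FDA 2007 scale, but diary entries are recorded against a CTCAE threshold and the SAP reports severity as CTCAE grade, with no separate solicited-event summary

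*Protocol*

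**What the plan says.** Two protocol sections give the grading scale for injection-site reactions, and they agree. Section 6.9: "When evaluating injection site reactions throughout the study, the investigator will be instructed to use the following grading scale in Table 13". Section 7.6: "The investigator will grade injection site reactions in accordance with September 2007 FDA Guidance for" Industry, the vaccine toxicity scale from which Table 13 is taken. Section 7.6 puts other clinical adverse events on CTCAE v4.03.

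Section 6.4.11 governs how the 7-day diary feeds the adverse event record. Two of its lines are local: "Pain and itching at injection site" and "Measure redness, swelling, bruising at injection site". Its rule is "Any PDC entry determined to meet the CTCAE criteria for a Grade 1 or higher adverse event should be" documented as an adverse event, unless it is part of ongoing medical history. Below that threshold, clinical judgment decides. If the diary entry and the final grade differ, the reason goes into source; no scale is given precedence.

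Secondary endpoint 1a is the incidence and severity of local and systemic events over 7 days, 28 days and the whole study. Protocol 8.5.3 asks for summaries by maximum severity without naming a scale. Protocol 7.15.1 says that certain events solicited in the 7 days after each dose will be summarized apart from the rest.

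The only severity-by-grade table in SAP 9.1 is "TEAEs, TEAEs with onset within 28 days/7 days after study treatment by Dose Number, CTCAE Grade, SOC and PT". The listings include one for treatment-emergent events of CTCAE Grade 3 or more. Neither Table 13 nor the FDA guidance appears in the SAP.

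**The concern.** A diary-reported local reaction meets one scale when the site decides whether to record it and another when the site grades it. The SAP then labels the resulting grade with the first scale. Two things are at stake, and they are separate.

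- **Incidence.** Whether a small reaction enters the adverse event data at all depends on whether the site works from 6.4.11 or from Table 13. That reaches the 7-day and 28-day rates and the between-arm risk differences in SAP 9.1.2.
- **Severity.** A grade assigned as 6.9 and 7.6 require would appear in a table headed CTCAE. A reader of the study report could not tell which scale a local Grade 2 or Grade 3 came from.

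Injection-site reactions are the expected local effect of injection with electroporation, so this concerns the main content of endpoint 1a rather than a rare event class.

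**Working it through.** The plan states no figure on this point and nothing can be recomputed. The check is to follow a local reaction through the text.

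| Step | Place | Scale |
|---|---|---|
| Diary entry becomes an adverse event | Protocol 6.4.11 | CTCAE Grade 1, otherwise judgment |
| Reaction is graded | Protocol 6.9, 7.6 | FDA 2007 (Table 13) |
| Grade is tabulated | SAP 9.1, TEAE table by grade | CTCAE |
| Grade 3 or more is listed | SAP 9.1, listings | CTCAE |
| Grade 3 or more is tabulated | SAP 9.1, Grade >=3 tables | none named |
| AESI is summarized | SAP 9.1.1 | none named |

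Three cases show the effect.

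1. **Redness of 2 cm in the diary.** The erythema row of Table 13 starts at 2.5 cm, so this has no grade there. Under 6.4.11 it is an adverse event if it meets CTCAE Grade 1; if not, judgment decides. The documents do not reproduce the CTCAE criteria, so the outcome cannot be fixed from them. Two sites can each follow a section of the protocol and reach different answers.

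2. **Itching or bruising at the site.** Both are diary items. Table 13 has rows only for pain, tenderness, erythema and induration/swelling. Sections 6.9 and 7.6 send these reactions to a scale with no row for them, while 6.4.11 sends them to CTCAE.

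3. **Redness above 10 cm.** Table 13 makes this Grade 3. A site that complies with 7.6 enters Grade 3 on the FDA scale. The SAP prints it in the CTCAE table and the CTCAE Grade >=3 listing. If the site had graded on CTCAE to match the SAP, it would have departed from 6.9 and 7.6. Neither route makes the output agree with the protocol.

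The collapsing rule in SAP 9.1 adds to case 3. A subject with several events at one MedDRA level is counted once, at the most severe. If an FDA-graded local reaction and a CTCAE-graded event fall in the same system organ class, the rule ranks grades from two scales against each other.

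For the solicited events, the SAP 9.1 table list has 7-day and 28-day onset windows, but no table separates solicited from unsolicited events. SAP Section 11, which records departures from the protocol's analyses, mentions only medical history. The omission is therefore not a declared change.

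**The case against.** The best defence is that 7.6 is the severity section and is clear: one scale per event class. Section 6.4.11 sets only a recording threshold and does not tell anyone to assign a final grade on CTCAE. The SAP label may be shorthand. SAP 9.1 allows further tables, SAP 4.4 lists all collected data, and the footnote to Table 13 has erythema recorded as a continuous measurement, so small diameters are recoverable. Treatment is blinded and placebo is also given with electroporation, so differences in site practice should not favour an arm. Endpoint 1a carries no formal hypothesis.

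Most of this stands, and it limits the point. It does not remove the conflict over what is recorded, correct the SAP label or supply the promised summary.

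Four stronger readings are tempting but unsupported.

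- **The dosing rules rest on two competing measures.** Section 4.3 says "Subjects who manifest Grade 4 toxicity attributable to the study treatment will be discontinued from the" study treatment, and names no scale; 7.14 names none either. But a Grade 1 recording threshold cannot move a reaction into Grade 3 or 4, an SAP column label cannot affect dosing, and the local reactions in 7.14 match the four rows of Table 13, which 7.6 already puts on the FDA scale. What remains is a missing cross-reference.
- **Tenderness goes unassessed until the next clinic visit.** Tenderness is not a named diary item, although it has a Table 13 row and protocol 3.5 names it among the common HPV-003 events: "administration-site reactions, which included pain, tenderness, erythema and swelling". But the calls 8 to 14 days after each dose include an injection-site evaluation (6.1.2). Only the daily diary item is missing.
- **The HPV-003 erythema rates (78% vs 57%) measure the problem.** That study used the frozen formulation, which was given with the earlier device. The documents do not say how its erythema was graded or what share was below 2.5 cm.
- **Every SAP severity output is CTCAE.** The Grade >=3 tables and the AESI section name no scale.

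**Conclusion.** The plan is wrong as written on a secondary safety endpoint. Followed exactly, it reports local severity under a scale the protocol does not assign to those events, leaves the recording threshold for small diary-reported reactions open to site practice, and omits a summary the protocol promises. All injection-site events in the by-grade table and the Grade >=3 listing are exposed to the labelling fault. The threshold fault concerns diary entries near or below the bottom of Table 13 and those with no row in it.

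How many subjects would change grade or drop out of the counts cannot be derived. That would need the CTCAE cut-points and the distribution of reaction sizes, and the documents give neither. The conclusion assumes that sites grade as 6.9 and 7.6 instruct and that the SAP tables are produced as listed. Primary efficacy is untouched. The point should be settled before database lock.

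**What to change.** 1. **Protocol 6.4.11.** Reconcile it with 6.9 and 7.6 so that one stated scale governs both recording and grading of diary-reported injection-site reactions. Say what applies to itching, bruising and reactions too small for a Table 13 grade.
2. **SAP 9.1.** Tabulate and list injection-site reactions by the scale on which they were graded, separately from CTCAE-graded events, including in the Grade >=3 outputs. Name the scale in each title.
3. **SAP 9.1.** Add the separate 7-day solicited-event summary from protocol 7.15.1, or declare its omission in Section 11.
4. **Minor.** Name in 4.3 and 7.14 the scale their grades refer to. Reconcile the diary list with Table 13 on tenderness.

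Which scale, threshold or dosing rule applies is for the sponsor to settle; the request is only that the sections agree.

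The cost is clarifying text, one extra set of tables and a check of grades already coded. If tenderness is added to the diary, cards completed earlier will lack it, and the report should say so.
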